9.2.2.2 Allodynia Symptoms Checklist 12 items (ASC-12)

The ASC-12 is a subject reported outcome measure used to assess the frequency of allodynia symptoms. The checklist will ask subjects to assess how often they experience increased pain or an unpleasant sensation on their skin during their most severe type of headache while engaging in each of the following: combing their hair, pulling their hair back (eg, ponytail), shaving their face, wearing eyeglasses, wearing contact lenses, wearing earrings, wearing a necklace, wearing tight clothing, taking a shower (when the shower water hits their face), resting their face or head on a pillow, exposure to heat (eg, cooking, washing their face with hot water), and exposure to cold (eg, using an ice pack, washing their face with cold water).

The subject answers each question using the following categories: “Does not apply to me”, “Never”, “Rarely”, “Less than half of the time”, “Half the time or more”. Responses to each question are assigned a score. A positive response to answer options 1 to 3 is scored as 0, a positive response to answer option 4 is scored as a 1, and a positive response to answer option 5 is scored a 2. The final grading is based on the sum of the 12 items.

Subjects will complete the ASC-12 using the eDiary.

9.2.2.3 Beck Depression Inventory (BDI-II)

The BDI-II is a 21-item questionnaire that assesses the severity of depression. Each item is scored from 0 to 3. The total score is categorized into 4 severity grades: minimal depression (0 to 13), mild depression (14 to 19), moderate depression (20 to 28), and severe depression (29 to 63). The BDI-II will be collected at the initial screening, baseline and DBTP periods. At initial screening, BDI-II will be collected in the electronic case report form (eCRF) for eligibility purposes only. The baseline period and DBTP BDI-II will be collected by eDiary.

Sites will be able to activate the baseline period BDI-II on the eDiary at the end of the subject’s baseline period, after at least 28 full calendar days have passed (inclusive of the day the subject was set-up on the eDiary device).

9.2.2.4 General Anxiety Disorder 7-item questionnaire (GAD-7)

The GAD-7 is a self-administered 7-item instrument that uses some of the DSM-V criteria for general anxiety disorder (GAD) to identify probable cases of GAD along with measuring anxiety symptom severity. Responders are asked to rate the frequency of anxiety symptoms in the last 2 weeks on a Likert scale ranging from 0 (‘not at all’) to

Approved

3 ('nearly every day'). Items are summed to provide a total score. Score interpretation is as follows: 1 to 4 minimal symptoms, 5 to 9 mild symptoms, 10 to 14 moderate symptoms, and 15 to 21 severe symptoms. Changes of 5 points or more are clinically meaningful.

9.2.2.5 Headache Impact Test-6 (HIT-6)

The HIT-6 is a short-form self-administered questionnaire based on the internet-HIT question pool. The HIT-6 was developed as a global measure of adverse headache impact to assess headache severity in the previous month and change in a subject's clinical status over a short period of time. Six questions cover severe pain, limitation of daily activity (household, work, school, and social), wanting to lie down when headache is experienced, feeling too tired to work or do daily activities because of headache, feeling "fed up" or irritated because of headache, and headache limiting ability to concentrate or work on daily activities. Each of the 6 questions is responded to using 1 of 5 response categories: "never", "rarely", "sometimes", "very often", or "always".

For each HIT-6 item, 6, 8, 10, 11, or 13 points, respectively, are assigned to the response provided. These points are summed to produce a total HIT-6 score that ranges from 36 to 78. The HIT-6 scores are categorized into 4 grades, representing little or no impact (49 or less), some impact (50 to 55), substantial impact (56 to 59), and severe impact (60 to 78) due to headache. No recall period is specified for the first 3 items. The recall period is the past 4 weeks for the last 3 items.

Subjects will complete the HIT-6 using the eDiary.

9.2.2.6 Migraine Disability Assessment Questionnaire (MIDAS)

The MIDAS Questionnaire is a 5-item self-administered questionnaire that sums the number of productive days lost over the past 3 months in 2 settings: the workplace and the home. The MIDAS also assesses disability in family, social, and leisure activities. The MIDAS score is the sum of missed days due to a headache from paid work, housework, and nonwork (family, social, leisure) activities; and days at paid work or housework where productivity was reduced by at least half. The recall period is 3 months.

The score is categorized into 4 severity grades: grade I = 0 to 5 (defined as minimal or infrequent disability), grade II = 6 to 10 (mild or infrequent disability), grade III = 11 to 20 (moderate disability), and grade IV = 21 and over (severe disability). Two other

questions (A and B) are not scored, but were designed to provide the physician with clinically relevant information on headache frequency and pain severity.

Subjects will complete the modified MIDAS using the eDiary.

9.2.2.7 Migraine Functional Impact Questionnaire (MFIQ)

The MFIQ is a self-administered 26-item instrument measuring the impact of migraine on broader functioning (ie, Physical, Social, and Emotional Functioning). It has 4 domains, Impact on Physical Functioning (5 items), Impact on Usual Activities (10 items), Impact on Social Functioning (5 items), and Impact on Emotional Functioning (5 items). In addition, there is 1 stand-alone global item assessing the overall impact on usual activities. Subjects respond to items using a 5-point scale assigned scores from 1 to 5, with 5 representing the greatest burden. The scores will be calculated as the sum of the item responses and the sum will be rescaled to a 0 - 100 scale, with higher scores representing greater burden. The recall period is the past 7 days.

Subjects will complete the MFIQ using the eDiary.

9.2.2.8 Migraine Physical Function Impact Diary (MPFID)

The MPFID is a self-administered 13-item instrument measuring physical functioning. It has 2 domains, Impact on Everyday Activities (7 items) and Physical Impairment (5 items), and 1 stand-alone global question which provides an assessment of overall impact on everyday activities.

Subjects respond to items using a 5-point scale, with difficulty items ranging from "Without any difficulty" to "Unable to do" and frequency items ranging from "None of the time" to "All of the time". These are assigned scores from 1 to 5, with 5 representing the greatest burden. For each domain, the scores will be calculated as the sum of the item responses and the sum will be rescaled to a 0 to 100 scale, with higher scores representing greater impact of migraine (ie, higher burden). There will be a score for each of the 2 domains and a third score for the stand-alone item. The recall period is the past 24 hours. Subjects will complete the MPFID daily using the eDiary.

9.2.2.9 Patient Global Impression of Change (PGIC)

The PGIC is a subject-reported outcome that evaluates general aspects of a subject's health and assesses if there has been an improvement or decline in clinical status. The PGIC employs a 7-point Likert scale that ranges from (1) 'Very much improved' to (7) 'Very much worse'. Subjects will complete the PGIC using the eDiary.

9.2.2.10 Sleep Questionnaire (ARMR sleep questionnaire)

The American Registry for Migraine Research (ARMR) sleep questionnaire is a novel self-administered 10-item patient-reported outcome that measures parameters of sleep quantity, sleep quality and daytime sleepiness and their relationship with migraine symptomatology and treatment over a 3-month recall period. Items 1 to 3 of the questionnaire evaluate parameters of sleep quantity as a discrete time variable. Items 4-6 and 8-10 evaluate several behaviors that denote poor sleep quality and excessive daytime sleepiness using a five-level Likert scale that ranges from 'strongly disagree' to 'strongly agree'. For each question, 'not applicable' options are also provided and are not scored. Each item may be scored separately or in combination within the same domain. Item 7 refers to lifetime sleep disorders history and will only be collected at day 1 post randomization visit.

Subjects will complete the ARMOR sleep questionnaire using the eDiary.

9.2.2.11 Health Resource Utilization Resource Questionnaire (HRU)

The questionnaire is designed to collect data on HRU. Specifically, the HRU questionnaire aims to capture frequency of **headache**-related inpatient hospitalizations and outpatient emergency department visits, urgent care visits, and other clinical visits. The recall period for the HRU questionnaire is 24 weeks. The questionnaire with the 24-week recall will be administered at day 1 and week 24 of the DBTP.

The HRU questionnaire assessed at the ET visit before week 24 should only include HRU recalled since the previous assessment to avoid collecting duplicate information. For example, the 24-week HRU questionnaire assessed at week 20 as the ET visit should only include HRU recalled since the previous assessment at day 1 (ie, 20-week recall).

HRU questionnaire is a clinician-reported outcome (CRO) to be collected at clinic visits through subject interview. The HRU data is to be inputted in the eCRF.

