^a The baseline period ends when either a subject is screen failed or randomized into the study. Randomization occurs at the Day 1 visit which must occur between 29 to 35 days after baseline entry (inclusive of the first day that eDiary device is assigned to subject).

^b On Day 1, all study assessments should be completed prior to subject's first dose of investigational product.

^c A subject who discontinues the study during the DBTP will complete the assessments of the week 24/ET visit approximately 28 (+3) days after the last dose of investigational product.

^d Including pre-filled syringe in DBTP and autoinjector during OLTP.

^e All clinical laboratory testing at screening (except pregnancy testing) will be performed at a central laboratory.

^f Additional on-treatment local laboratory pregnancy testing may be performed at the investigator's discretion if there is suspicion that a female subject is pregnant or per local laws and regulations.

^g For subjects who provided informed consent for the pharmacogenetic studies, DNA will be obtained from residual cells from the biomarker blood sample. Therefore, additional sampling is not required.

^h The BDI-II will be collected via paper CRF during screening and eDiary thereafter.

ⁱ The Baseline Period BDI-II will be completed at the end of the Baseline Period using the eDiary, after at least 28 days of data has been entered in the eDiary.

Approved

Product: Erenumab
Protocol Number: 20170703
Date: 27 May 2020

J The baseline HRU questionnaire will have a 24-week recall of prior utilization. The HRU questionnaire assessed at the ET visit before week 24 should only include HRU recalled since the previous assessment to avoid collecting duplicate information. For example, the 24-week HRU questionnaire assessed at week 20 as the ET visit should only include HRU recalled since the previous assessment at day 1 (ie, 20-week recall).

Approved

Table 2-2. Schedule of Activities - Study Visits Through Open-label Treatment Period

	Treatment Period								
	Open-label Treatment Period (28 Weeks)								
PROCEDURE	Wk 24 (OLTP Entry Visit)	Wk 28	Wk 32	Wk 36	Wk 40	Wk 44	Wk48	Wk 52/ EOS ^a	Notes
GENERAL AND SAFETY ASSESSMENTS									
Clinic Visit	X	X			X			X	
Telephone Contact			X	X		X	X		
IRT call ^b	X	X			X			X	
Physical examination	X				X			X	
Vital signs	X				X			X	BP, HR, RR, and temperature
Adverse events	X	X	X	X	X	X	X	X	
Serious adverse events	X	X	X	X	X	X	X	X	
Adverse device effects ^c	X	X	X	X	X	X	X	X	

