
 To explore migraine-related disability metrics as measured by the migraine functional impact questionnaire (MFIQ) 	
 Change from baseline in MFIQ domain scores and overall impact on usual activities global item score at assessment time points

 To explore migraine-related disability and productivity as measured by the Migraine Disability Assessment (MIDAS) Questionnaire 	
 Change from baseline in MIDAS total score, absenteeism score and presenteeism score at assessment time points during DBTP Cumulative (sum of) changes from baseline in MIDAS total score, absenteeism score and presenteeism score over 6 months during DBTP

 To explore the effect of erenumab compared with placebo on the change from baseline in health resource utilization (HRU) 	
 Occurrence of at least 1 headache-related hospitalization or outpatient HRU during the DBTP Occurrence of at least 1 headache-related hospitalization during the DBTP Occurrence of at least 1 headache-related outpatient HRU during the DBTP Occurrence of at least 1 headache-related outpatient emergency room visit during the DBTP Occurrence of at least 1 headache-related outpatient urgent care visit during the DBTP

Approved

Objectives	Endpoints
	
 • Occurrence of at least 1 headache-related outpatient clinic visit during the DBTP

 • To explore the effect of erenumab compared with placebo on the change from baseline in depression and anxiety symptoms 	
 • Change from baseline in Generalized Anxiety Disorder 7-item scale (GAD-7) score at assessment time points • Change from baseline in Beck Depression Inventory-II (BDI-II) score at assessment time points

 • To explore the effect of erenumab compared with placebo on the change from baseline in measures of sleep quality 	
 • Change from baseline in each of the sleep questionnaire domain scores at assessment time points

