4.1 Planned Covariates

All model-adjusted analyses of efficacy endpoints in nonopioid-treated cohort will include the following covariates:

- Concomitant oral migraine preventive treatment initiated before screening AND taken during baseline (Yes or No)
- Corresponding baseline value for the endpoint being analyzed (for continuous endpoints only)

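### The exploratory HRU objective is change from baseline, but all six HRU endpoints are post-baseline yes/no items, and no specified model uses the visit counts or the 24-week baseline

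*Protocol*

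**What the plan says.** Protocol 4.1, repeated in SAP 2.1, states the objective: "To explore the effect of erenumab compared with placebo on the change from baseline in health resource utilization (HRU"). Six endpoints follow. The first is "Occurrence of at least 1 headache-related hospitalization or outpatient HRU during the DBTP" and the last is "Occurrence of at least 1 headache-related outpatient clinic visit during the DBTP"; the four between have the same form.

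On the instrument, Protocol 9.2.2.11 says that "the HRU questionnaire aims to capture frequency of" headache-related hospital stays and emergency, urgent-care and other clinical visits. On timing it says: "The questionnaire with the 24-week recall will be administered at day 1 and week 24 of the DBTP". The footnote to Protocol Table 2-1 adds: "The baseline HRU questionnaire will have a 24-week recall of prior utilization". A subject who terminates before week 24 reports only the time since day 1.

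SAP Table 5-6 defines a Day 1 (Baseline) window and a Week 24 window for HRU, and SAP 8.3 gives a rule for incomplete HRU dates. For the analysis, Protocol 10.4.2.2 sends dichotomized exploratory endpoints to a stratified CMH test, and SAP 9.5.3 refers back to the methods for the primary and secondary endpoints. Protocol 10.2.2 lists the baseline value as a covariate without restriction. SAP 4.1 narrows it: "Corresponding baseline value for the endpoint being analyzed (for continuous endpoints only"). SAP 9.4 does not list HRU among the baseline characteristics. SAP 9.7.1 describes the questionnaire and names no analysis.

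**The concern.** The objective and the endpoints ask different questions. The objective is about change. The data needed for change are collected: a frequency on day 1 and a frequency at week 24, over equal 24-week spans for subjects who reach week 24. The endpoints then drop both the frequency and the baseline.

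Two things are at stake. First, the report would have no specified result for the change-from-baseline part of the objective. Second, the yes/no cut discards information: a subject who goes from four clinic visits to one is scored the same as a subject who stays at four. If visits are common, a real reduction could be missed.

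**Working it through.** **1. The texts side by side.**

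| Element | Uses baseline? | Uses counts? |
|---|---|---|
| Objective (Protocol 4.1, SAP 2.1) | Yes, change from baseline | Not stated |
| Questionnaire (Protocol 9.2.2.11, Table 2-1 footnote) | Yes, 24-week prior recall | Yes, frequency |
| Visit windows (SAP Table 5-6) | Yes, Day 1 window | Not applicable |
| Six endpoints (Protocol 4.1, SAP 2.1) | No | No, at least one event |
| Test (Protocol 10.4.2.2, SAP 9.5.3) | No, stratified on oral preventive use only | No |
| SAP 9.7.1 | No analysis named | No analysis named |

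**2. The plan's own power figure.** No power is stated for HRU. The only stated figures are for the primary endpoint (Protocol 10.1): 33.1%, 50.5% and 64.1% on placebo, 70 mg and 140 mg, 183 per arm, 20% dropout, two-sided 0.05. I used

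z = [|p1 − p2|·√n − 1.96·√(2·p̄(1 − p̄))] / √(p1(1 − p1) + p2(1 − p2)), power = Φ(z), with n = 183 × 0.80 = 146.4.

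- 70 mg: (0.174 × 12.10 − 1.96 × 0.6975) / 0.6866 = 1.075, power 85.9% (stated 85%).
- 140 mg: (0.310 × 12.10 − 1.96 × 0.7068) / 0.6720 = 3.52, power 99.98% (stated > 99%).

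The plan's figures reproduce, so the same formula can serve for the yes/no HRU test.

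**3. Yes/no power under assumed visit rates.** Everything here about HRU is an assumption, because the documents give no value. Visit counts are taken as Poisson with gamma frailty: placebo mean μ per 24 weeks, rate ratio 0.70, dispersion φ = 1 or 2. The proportion with at least one visit is 1 − (1 + φμ)^(−1/φ). For μ = 1 and 183 per arm:

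- φ = 1: 50.0% on placebo, 41.2% on active. z = (0.0882 × 13.53 − 1.96 × 0.7044) / 0.7016 = −0.27, power about 39%.
- φ = 2: 42.3% and 35.5%. z = (0.0682 × 13.53 − 1.96 × 0.6893) / 0.6876 = −0.62, power about 27%.

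These agree with the simulated 26-41% in step 4.

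**4. Comparison with a count model.** Simulation, 600 runs per setting, one active arm versus placebo, 183 per arm, rate ratio 0.70, φ = 1 or 2, frailty 50% or 100% shared between the baseline and follow-up periods. The count model is a Poisson regression with robust standard errors, adjusted for baseline.

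| Placebo mean visits per 24 weeks | Yes/no test | Count model with baseline |
|---|---|---|
| 0.1 | 15-17% | 15-17% |
| 0.3 | 21-31% | 28-37% |
| 0.5 | 24-34% | 38-51% |
| 1 | 26-41% | 56-76% |
| 2 | 25-38% | 63-93% |
| 3 | 21-36% | 68-99% |

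With 600 runs the simulation standard error is at most √(0.25/600) = 2 percentage points. At 146 per arm the pattern is the same: at mean 1, 23-35% versus 44-65%. The simulation gives every subject equal 24-week periods and does not model the shorter recall of early terminators.

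**The case against.** Several objections have force.

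- **A reader might infer that the HRU objective is not addressed at all.** The documents do not support that. A randomized comparison of occurrence during the DBTP estimates an effect on HRU, and randomization supplies comparability at baseline. Only the change-from-baseline part is missing, and rewording the objective would also remove the mismatch.
- **A reader might infer that power is roughly halved for outpatient use.** No rate, dispersion or effect is given, so this cannot be said of this trial. In the table the loss is nil at 0.1 visits, about half near 1 visit, and more than half at 2 or above.
- **A reader might infer that the yes/no item sits near its ceiling.** No passage gives the proportion with a visit. Under the assumed model it is 42-50% on placebo at mean 1, and 62-75% even at mean 3.
- **Baseline and counts are not wholly unused.** SAP 9.1 plans summaries by treatment group and visit, and Table 5-6 defines both HRU visits, so a descriptive baseline summary is a fair reading. Protocol 9.2.11 says that encounter data in the case report form may support exploratory economic analyses. Both are permissive or generic, and neither specifies a model.
- **SAP 9.7.1 does not leave HRU without an analysis.** SAP 9.5.3 routes the six endpoints to CMH.
- **The recall spans match only for subjects who reach week 24.** That is correct. It is a reason for a time offset in any count analysis; the CMH test makes no such adjustment either.

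What stands is narrower: the wording mismatch, and the absence of any specified model for the counts or the baseline.

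**Conclusion.** The point holds in limited form. The objective names change from baseline, the data for it are collected, and all six endpoints and their test leave it out. That rests on the text alone.

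The size of any loss of power rests on assumed visit means, dispersion and a rate ratio of 0.70. Within those assumptions the count model had power at least comparable to the yes/no test in every setting. It was clearly better once placebo subjects average about 0.5 visits or more per 24 weeks. For rare events such as hospital stays, little or nothing would be gained.

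Severity is minor. HRU is exploratory, lies outside the fixed testing sequence, and has no stated power, so no confirmatory conclusion depends on it.

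**What to change.** In SAP 9.5.3 or 9.7.1, add an exploratory analysis of the number of headache-related encounters (total, and outpatient) in the DBTP:

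- Negative binomial or robust Poisson regression with treatment, the stratification factor and log(baseline count + 1).
- An offset for log weeks covered, so that early terminators contribute for the time they report.
- The rate ratio versus placebo with 95% CI for each dose.
- Baseline counts and change from baseline summarised by arm.
- The six occurrence endpoints kept as they are.

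If the sponsor prefers not to add a model, the minimum is to reword the objective to occurrence during the DBTP, or to add the summary of baseline and change.

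The cost is SAP wording and one extra exploratory model on data already collected. Hospitalization and emergency counts are probably too sparse to model separately and would stay descriptive.

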9.2.3 Safety Assessments

Planned time points for all safety assessments are listed in the Schedule of Activities see ([Table 2-1](#)).

Approved

9.2.3.1 Adverse Events

9.2.3.1.1 Time Period and Frequency for Collecting and Reporting Safety Event Information

9.2.3.1.1.1 Adverse Events

Adverse events related to any study procedures/study-activity are reported **after the first dose of investigational product**. All other adverse events are reported after the first dose of investigational product.

The investigator is responsible for ensuring that all adverse events observed by the investigator or reported by the subject that occur after first dose of investigational product through the end of study are reported using the Event CRF.

The adverse event grading scale to be used for this study will be the Common Terminology Criteria for Adverse Events (CTCAE) and is described in [Section 12.4](#).

9.2.3.1.1.2 Serious Adverse Events

The investigator is responsible for ensuring that all serious adverse events observed by the investigator or reported by the subject that occur after **signing of the informed consent** through the end of study are reported using the Event CRF.

All serious adverse events will be collected, recorded and reported to the sponsor or designee within 24 hours, as indicated in [Section 12.4](#). The investigator will submit any updated serious adverse event data to the sponsor within 24 hours of it being available.

The criteria for grade 4 in the CTCAE grading scale differs from the regulatory criteria for serious adverse events. It is left to the investigator's judgment to report these grade 4 abnormalities as serious adverse events.

9.2.3.1.1.3 Serious Adverse Events After the Protocol-required Reporting Period

There is no requirement to monitor study subjects for serious adverse events following the protocol-required reporting period or after end of study. However, these serious adverse events can be reported to Amgen. Per local requirements in some countries, investigators are required to report serious adverse events that they become aware of after end of study. If serious adverse events are reported, the investigator is to report them to Amgen within 24 hours following the investigator's knowledge of the event.

Serious adverse events reported outside of the protocol-required reporting period will be captured within the safety database as clinical trial cases and handled accordingly based on relationship to investigational product.

Approved

The method of recording, evaluating, and assessing causality of adverse events, and serious adverse events and the procedures for completing and transmitting serious adverse event reports are provided in [Section 12.4](#).

